The need for developing oncogene receptor specific agents, such as those proposed here, is compelling. The primary tools for PC screening, the serum PSA and the digital rectal examination are neither specific nor sensitive, as many men with elevated PSA have been found not to have PC [2]. Transrectal ultrasonography (TRUS) provides an axial and sagital examination of the prostate gland, and allows physicians to estimate its volume. However, in 60-70% of PC cases are hypoechoic and thus invisible by TRUS [3]. Histologic examination, therefore, remains the gold standard for PC but requires an invasive procedure for tissue sampling. By this time, the PC is usually advanced. However, the question still remains as to where to direct the needle for biopsy. As a result, out of the approximately 750,000 prostate biopsies that will be performed in the USA in 2010, more than 2/3 will find benign pathology [17].

The use of contrast enhanced spiral computerized x-ray tomography (CT) is limited to advanced, high-grade tumors [18]. Using 3D MR spectroscopic imaging, PC was diagnosed as possible if the ratio of choline to citrate exceeded 2SD above the normal population and definite if the ratio exceeded 3SD above the normal population [19]. However, sensitivity and specificity were only 80% and 46%, respectively [20]. Dynamic contrast enhanced MRI (DCE-MRI) is known to be a powerful tool for localization of vascular solid tumors [21].

DCE-MRI however has low sensitivity (50%) [22] and has not been able to distinguish between PC and benign prostatic hyperplasia (BPH) [23]. T2 weighted endorectal MRI also has low accuracy of PC detection [24]. Much more work therefore, is needed to be done [25].

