lesions. We expect that VPAC1 receptor specificity will differentiate malignant lesions from benign masses noninvasively, Unequivocal identification of PC lesions could help physicians tailor an appropriate therapeutic intervention. The anticipated reduction in false positives and false negatives should reduce morbidity and mortality, and improve the quality of life of PC patients. This novel approach to image PC by targeting a gene product is hypothesis-driven and based upon our own experience and the wealth of information yielded by recent advances in genomics and proteomics. When prostate cells undergo genomic modulations for whatever reason, they overexpress VPAC1 cell surface receptors. These changes occur well ahead of shed PSA or cell-morphologic alterations, the histology of which forms the basis of current PC diagnosis. The specificity of genomic biomarkers, should permit us to image PC in patients.

Biological fluids, including urine, represent a promising source of biomarkers for detection and prediction of PC prognosis. Because urine is available non-invasively and readily, numerous studies targeting DNA, RNA, protein and metabolite based biomarkers have been performed. However, none have yet reached the clinic]. Even FDA approved PCA3 test has low sensitivity and limitations in predicting aggressive PC.

VPAC1 cell surface genomic receptors are over-expressed at the onset of the malignancy, prior to elevation of PSA, and well before cell morphology is altered . We hypothesized that VPAC1 receptors expressed in high density on PC can be targeted for detection of shed tumor cells (STC) in patient urine, using TP4303, a VPAC1 specific biomolecule labeled with a near infrared fluorophore.

The success of these goals will meet the compelling need to a) localize primary PC, that can guide biopsy procedures. b) detect recurrent disease and c) image metastatic lesions with improved reliability. Reliable detection of PC can reduce the need for invasive biopsies, and minimize overtreatment, including surgery. It is important to note that overtreatment can cause incontinence or impotence. Thus, VPAC1 imaging addresses serious healthcare issues that current approaches cannot resolve, despite the great strides made in recent decades.

The results of our previous translational research and early applications in

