Methods: 25 men scheduled for radical prostatectomy and who signed IRB approved consent form were PET imaged preoperatively. Standardized Uptake Values (SUVs) were determined, malignant lesions (SUV > 1.0) were counted, and data compared with histologic findings. In addition, de-paraffinized whole mount pathology slides (n=68) from 6 VPAC1 PET imaged patients, 3 benign prostatic hyperplasia (BPH) patients (n=9), one malignant lymph node (n=3), and one benign lymph node (n=3) were incubated with ⁶⁴Cu-TP3805, washed with PBS, dried and subjected to digital autoradiography (DAR). Slides were then H&E stained, read by a pathologist, and DAR images were compared with foci delineated as PC, benign, cyst, or prostatic intraepithelial neoplasia (PIN).

Results: In 25 patients, 212 lesions had SUVs > 1.0 as compared to 127 lesions identified by histology. While the status of the remaining 85 PET lesions remains to be determined, in 68 histological slides from 6 PET imaged patients, DAR identified 105/107 PC foci (missed 2 due to artifact), 19/19 high grade PIN (HGPIN), 2/2 ejaculatory ducts (ED) and 5/5 urethra verumontanum (UV). Additionally, DAR found 9 PC lesions not previously identified by histology. The positive and the benign lymph nodes were correctly identified by DAR, and for the 3/3 BPH patients without PC, and 5/5 cysts, DAR was negative.

Conclusion: ⁶⁴Cu-TP3805, a VPAC1 receptor specific biomolecule delineates PC lesions in vivo and ex vivo, provides normal images for benign masses, and is worthy of further studies in patients.

In this investigation, we will use the same preparation, Cu-64-TP3805 that has been prepared and used in the previous human subjects with 100% success. Although no preparation will either be compounded or used out of the Jefferson campus, we will use a "kit" that will be ready to be heated following the

addition of 440 μ L of sterile H2O and then Cu-64 activity. These kits will contain all chemicals in sterile, 10 mL glass vials. Reagents will be added to the vial, snap frozen in dry ice, lyophilized and the vials will be sealed in N2 atmosphere. They will be stored at 4°C and examined for Cu-64 labeling and shelf life stability.

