3.2 Primary Study Endpoints

The primary endpoint of study will be to determine the ability of Cu-64-TP3805 to detect PC foci within the prostate gland in patients with persistialy elevated PSA as compared with tumor maps derived by histology of biopsy specimens obtained guided biopsy.

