7.0 STATISTICAL PLAN

7.1 Sample Size Determination

7.2 We will study 20 patients with persistently elevated PSA for a Cu-64 PET imaging in whom biopsy are ordered. These patients shall be PET imaged with our Cu-64 peptide probe first and then a week or so later the image guided biopsy shall be performed. The image guided biopsy is the standard of care procedure. The objective is to validate the PET imaging results with the histology of biopsy results. Generally, approximately 60% of the patients with elevated PSA have prostate cancer. We expect 80% accuracy in identifying 20 subjects as having histologically determined cancer/absence of cancer. The 95% confidence interval of this level of accuracy for this sample size is + or – 17.5%. Thus we expect to find an accuracy level between 62.5% to 97.5%. Please note this is a pilot study, not designed to be an efficacy determination trial. **Statistical Methods**

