15.0 APPENDICES

Include any attachments for this study (e.g. study schedule/visit chart from procedures section, Pill Diaries to be used, recruitment materials if applicable, AE Logs from section 5.2, Eligibility Checklist, Drug Reconciliation Form, etc.)

15.1 Visit Chart:

Subject with persistently high PSA seeing a Urologic Oncologist at Jefferson (Drs. [name], [name] or [name]) and is scheduled for MRI fusion/trans rectal ultrasound (TRUS) prostate biopsy.

Screening Visit:

- Clinical coordinator reviews chart and interviews patient
- Clinical coordinator confirms subject eligibility
- Subject signs informed consent

Imaging Visit:

- Clinical coordinator meets patient in Radiology
- Vitals signs are monitored before and after imaging procedure
- Intravenous catheter inserted and study agent (Cu-64-TP3805) infused
- PET imaging procedure completed
- Follow up call 24 hours later to ensure absence of adverse event

MRI fusion/TURS Date:

- At least one week but not more than 3 weeks later
- Biopsy complete and pathology results received
- Subject completion of protocol

15.2 Case Report forms:

Cu-64-TP3805

PET Imaging Date: MRI fusion/TURS Biopsy Date:									
Study #									
			Surge	on:					
Patient Identification:									
Patient Initials:						Medical Record #:			
Body Weight:						Age:			
Ethnic	ity:		Cauca	sian			African American		
	□ Asian					Latino			
Inclusion Criteria:									
	Intermediate/High Risk Disease (must check at least one box):								
	PSA :				.		PSA ≥10 ng/DL		
	DRE:					_	T2b, T2C, T3 or T4		
	Signature:								

StudyCu-64 Date:	4-TP3805 PET Scan results
Patient INT'	"L
Study #	
Interpreting	Radiologist:
Prostate Se	extant Visible Foci:
□ L Base	SUV:
	Size: x x mm
□ L Mid	SUV:
	Size: x x mm
□ L Apex	SUV:
	Size: x x mm
	Signature:

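### Per-subject accuracy is judged against one biopsy not directed by PET, with no later verification, so it is biased, probably but not certainly downward, and PET errors cannot be told from needle errors.

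*Combined protocol and SAP*

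**What the plan says.** Section 7.1 sets the one quantified target: "We expect 80% accuracy in identifying 20 subjects as having histologically determined cancer/absence of cancer". This is a per-subject measure. Section 3.2 words the primary endpoint at the level of foci, "as compared with tumor maps derived by histology of biopsy specimens obtained guided biopsy". In both places the reference is histology from the guided biopsy and nothing else.

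Sections 6.1 and 15.1 identify that biopsy as the MRI fusion/TRUS procedure, one to three weeks after PET, and section 7.1 calls it standard of care. No step directs a core to a PET focus. The visit chart in section 15.1 reads "Biopsy complete and pathology results received" and then records completion of the protocol. The only other follow-up is the 24-hour safety call (sections 6.1 and 8.1). Section 7 has no rule for men who are PET-positive and biopsy-negative.

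Section 7.3 analyses men who were imaged and biopsied. Section 4.5.1 withdraws, and leaves out of the analysis, men who do not have a radical prostatectomy.

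**The concern.** The protocol gives its own reasons to doubt that a negative biopsy means no cancer. On targeting, section 1.2 says "However, the question still remains as to where to direct the needle for biopsy". On timing, it says of VPAC1 expression "These changes occur well ahead of shed PSA or cell-morphologic alterations, the histology of which forms the basis of current PC diagnosis". In the prostatectomy series in section 1.8, PET showed 212 lesions against 127 on histology, and the status of the other 85 was unresolved. The same section reports "Additionally, DAR found 9 PC lesions not previously identified by histology".

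If the agent finds cancer that the needle misses, the plan records that as an error. If the agent lights up benign tissue, the plan records the same thing. With participation closed at the pathology report, the trial cannot separate the two. With 20 men, each reclassified man moves accuracy by 1/20 = 5 points.

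**Working it through.** **The plan's own figure.** Section 7.1 says "The 95% confidence interval of this level of accuracy for this sample size is + or – 17.5" percentage points. The usual normal-approximation interval gives 1.96 × √(0.8 × 0.2 / 20) = 0.1753, or 62.5% to 97.5%. The figure reproduces. It covers sampling error only, so the issue is the reference standard and not the arithmetic.

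**Inputs.** From section 7.1: n = 20, accuracy 80%, prevalence π about 60%. Assumed, because the documents do not give them: biopsy miss rate m among men with cancer (10%, 20%, 30%); PET sensitivity and specificity of 80% each, which is one way to reach 80% accuracy; biopsy never falsely positive.

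**Formula.** A fraction πm of men have a cancer that the needle misses. PET is positive in a share s of them: truly correct, scored wrong. PET is negative in the share 1 − s: truly wrong, scored correct. Hence

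apparent − true accuracy = −πms + πm(1 − s) = −πm(2s − 1).

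**Independent errors (s = 0.8, π = 0.6).**

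| m | Bias | Apparent accuracy | Net men of 20 |
|---|---|---|---|
| 10% | −0.6 × 0.1 × 0.6 = −3.6 points | 76.4% | 0.7 |
| 20% | −0.6 × 0.2 × 0.6 = −7.2 points | 72.8% | 1.4 |
| 30% | −0.6 × 0.3 × 0.6 = −10.8 points | 69.2% | 2.2 |

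**Dependence on s (π = 0.6).**

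| s | m = 10% | m = 20% | m = 30% |
|---|---|---|---|
| 1 | −6 | −12 | −18 |
| 0.5 | 0 | 0 | 0 |
| 0.3 | +2.4 | +4.8 | +7.2 |
| 0 | +6 | +12 | +18 |

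**Why downward is the likelier direction.** At 80% accuracy and 60% prevalence, PET sensitivity is lowest when specificity is 100%: (0.8 − 0.4)/0.6 = 66.7%. If PET and needle miss cancers independently, s is at least 0.667, above 0.5, and the bias is negative: −0.6 × 0.1 × 0.333 = −2.0 points at the smallest and −0.6 × 0.3 × 1 = −18.0 at the largest. If both tend to miss the same cancers, s can fall below 0.5 and the sign turns.

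**Other prevalences.** Section 1.2 says more than 65% of biopsies are benign. With π = 35% and 80%/80%, the bias is −2.1, −4.2 and −6.3 points. If the 60% means biopsy-positive men, the needle-missed fraction is 0.6m/(1 − m), and the bias at s = 0.8 is −4.0, −9.0 and −15.4 points.

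**The case against.** **Direction.** A reader might infer that accuracy must be understated. The documents do not support that. Cancers missed by both methods are credited as correct negatives, and nothing shows that the two sets of errors are independent. Section 1.2 concedes that 4–6 mm scanner resolution may be a problem, although it expects small lesions to be seen.

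**The earlier series.** A reader might take 85 of 212 as a 40% rate of PET lesions without a histologic match. It is only the difference between two counts; no lesion-by-lesion matching is reported. Nor are the 9 extra cancers PET findings: they come from ex vivo autoradiography, with the slides of PET-imaged men coming from six patients. The same slides were positive in 19 high-grade PIN foci, 2 ejaculatory ducts and 5 verumontanum sites, which is 26 non-cancer foci. True PET false positives are therefore a documented possibility. The series gives no per-subject biopsy miss rate.

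**Units.** The 80% is per subject. An unsampled PET focus in a man whose biopsy is positive elsewhere does not make him an error. The focus-level problem arises only if the endpoint in section 3.2 is analysed by focus or sextant, for which no rule is given.

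**Scope.** The plan calls the comparison histological, calls histology the gold standard, and says the pilot is not meant to establish efficacy. That limits the seriousness but does not remove the point, since accuracy is the only quantified result.

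**Who is scored.** If section 4.5.1 applied, most biopsy-negative men would probably drop out, and with them most of this bias and most of the information on specificity. The scoring is not settled until sections 4.5.1 and 7.3 agree.

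**Conclusion.** The point holds in this form: accuracy against one biopsy is a biased measure of accuracy for cancer, probably but not certainly downward, and the plan as written cannot tell a false-positive PET from a false-negative biopsy. At the plan's 80% and 60%, with 80%/80% and independent errors, the loss is 3.6 to 10.8 points for assumed miss rates of 10% to 30%. That is smaller than the 17.5-point half-width, but it is systematic: the interval does not reflect it, and more men would not reduce it. The miss rates are assumptions, and the size cannot be derived from the documents. The sign rests on s being above 0.5. The discordance in section 1.8 is real but could go either way, so it supports verifying discordant results rather than presuming that PET is right.

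**What to change.** 1. **Sections 3.2 and 7.** Report the primary per-subject result as agreement with first biopsy, and list PET-positive/biopsy-negative men separately. For any focus or sextant analysis, treat a PET-positive sextant with no core as not evaluable. The case report form already records PET by sextant; core locations are needed in the same units.

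2. **Sections 6.1 and 15.1.** Replace completion at the pathology report with passive chart review of routine-care results (repeat biopsy, prostatectomy pathology, PSA) for all 20 men, whatever their PET or biopsy result, to a fixed cut-off. Report accuracy against best available histology as a pre-specified secondary analysis. Do not restrict the review to PET-positive/biopsy-negative men: that can turn PET errors into successes but never uncover a PET-negative cancer, so accuracy could only rise.

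3. **Section 7.** Add a sensitivity analysis. With observed biopsy-positive fraction b, adjusted accuracy = observed accuracy + [b × m/(1 − m)] × (2s − 1), tabulated over assumed m (for example 10% to 30%) and over s on both sides of 0.5.

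4. **Sections 4.5.1 and 7.3.** Reconcile the two statements of who is analysed.

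Cost: consent and HIPAA wording and review of 20 charts, with no added visit, procedure or reader. Later verification will be incomplete, will depend on routine care and will be shorter for late enrollees, so it stays secondary. Some sextants will leave any focus-level denominator.

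### Section 7 measures only whether each man is correctly called cancer or no cancer, with no location criterion, although the primary endpoint in 3.2 is detection of cancer foci against biopsy tumor maps.

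*Combined protocol and SAP*

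**What the plan says.** Section 7.1 sizes the study on a single quantity: "We expect 80% accuracy in identifying 20 subjects as having histologically determined cancer/absence of cancer". The precision statement follows: "The 95% confidence interval of this level of accuracy for this sample size is + or – 17.5" percentage points, and "Thus we expect to find an accuracy level between 62.5% to 97.5" percent. The Study Summary repeats this under Statistical Methodology. The Statistical Methods heading at the end of that text has nothing under it, so Section 7 contains no definition of a positive PET scan and no rule for matching PET to biopsy by site.

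Elsewhere the protocol does deal with location:

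- Section 3.2 makes the primary endpoint the detection of cancer foci in the prostate, "as compared with tumor maps derived by histology of biopsy specimens".
- The schema in the Study Summary says PET will be compared with biopsy pathology for both detection and localization of foci.
- The PET results form in 15.2 records visible foci by prostate sextant, with SUV and size.

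The primary objective in 2.1 is worded more loosely, as detecting prostate cancer in men with persistently elevated PSA.

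**The concern.** The endpoint is about foci and the analysis is about men. Suppose PET shows one focus at the left base and the biopsy finds cancer only at the right apex. For the endpoint in 3.2 this is a missed cancer plus a focus with no cancer found there. Under a cancer/absence call per man, with no location criterion, it is one correct identification.

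The reported accuracy could therefore look satisfactory without answering 3.2 or the localization aim in the schema. The data needed on the PET side are already planned, but no analysis in Section 7 uses them.

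**Working it through.** **Inputs**

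- Sample size 20: "We will study 20 patients with persistently elevated PSA for a Cu-64 PET imaging in whom biopsy are ordered" (7.1).
- Expected accuracy 0.80: "We expect 80% accuracy in identifying 20 subjects" (7.1), which is 16 of 20.
- Prevalence about 60%: "Generally, approximately 60% of the patients with elevated PSA have prostate cancer" (7.1), which is 12 men with cancer and 8 without.
- Rate of wrong-site uptake: not given in the documents, so it is varied below as an assumption.

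**Step 1. Reproduce the plan's figure.** Two-sided 95% Wald half-width: 1.96 × √(0.80 × 0.20 / 20) = 0.1753, giving 62.5% to 97.5%. The plan's arithmetic is right. Other intervals for 16/20 do not give the stated limits (Wilson 58.4% to 91.9%, Clopper-Pearson 56.3% to 94.3%). The denominator that reproduces the figure is 20 men, which confirms that the planned unit is one call per man and not foci or sextants.

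**Step 2. Add a location criterion.** Let m be the number of men with cancer who are PET-positive only away from the biopsy-proven site. Men without cancer are scored as before. Sixteen correct calls could be, for example, 10 true positives plus 6 true negatives, 12 plus 4, or 8 plus 8. In each case:

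matched accuracy = (16 − m) / 20, half-width = 1.96 × √(p(1 − p)/20).

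| m (assumed) | Section 7 accuracy | Matched accuracy | Wald half-width (points) |
|---|---|---|---|
| 0 | 80% | 80% | 17.5 |
| 1 | 80% | 75% | 19.0 |
| 2 | 80% | 70% | 20.1 |
| 3 | 80% | 65% | 20.9 |
| 4 | 80% | 60% | 21.5 |
| 5 | 80% | 55% | 21.8 |

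Each wrong-site man costs 1/20 = 5 points, and the Section 7 figure does not move.

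**Step 3. How far a sextant match can be trusted.** Assume PET marks u distinct sextants of 6 at random and cancer occupies c sextants. The chance of at least one match is 1 − C(6−c, u)/C(6, u).

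| | u = 1 | u = 2 | u = 3 |
|---|---|---|---|
| c = 1 | 17% | 33% | 50% |
| c = 2 | 33% | 60% | 80% |

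With many foci, chance matching becomes the rule. The earlier series in 1.8 reports: "In 25 patients, 212 lesions had SUVs > 1.0 as compared to 127 lesions identified by histology". That is 212/25 = 8.48 PET foci per man. If that many foci each fell in a sextant at random, the chance of a match would be 1 − (5/6)^8.48 = 79% for cancer in one sextant and 1 − (4/6)^8.48 = 97% for two. Matching reduces coincidental credit but does not remove it, so the number of PET-positive sextants per man has to be reported with it.

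**The case against.** **Section 7 does not state a scoring rule.** True. That wrong-site uptake would be credited is inferred from the binary man-level definition and the absence of any location criterion. This limits the wording of the point; it also supports writing the rule down.

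**Man-level accuracy is a legitimate measure.** It is. Objective 2.1 can fairly be read at man level, and Section 7 fits that reading. It does not fit 3.2 or the schema, which is why the man-level figure should be kept and supplemented.

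**A reader might infer that a high accuracy would say nothing about detection.** The documents do not support this. If PET is positive with probability P regardless of cancer status, expected accuracy is 0.6P + 0.4(1 − P) = 0.4 + 0.2P, at most 60%. That is below both the expected 80% and the plan's lower limit of 62.5%, so man-level accuracy already exposes a scan unrelated to cancer. The gap concerns individual men with cancer whose uptake is elsewhere.

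**A reader might also infer from 1.8 that unrelated foci are common.** The 212 − 127 = 85 PET lesions (40%) without a histologic counterpart are described as unresolved, not as false. Autoradiography on slides from 6 of those men found 9 cancers that histology had not identified, and it also marked high-grade PIN and some normal structures. The men were prostatectomy candidates, a different population. The series shows that wrong-site uptake is possible; it gives no rate.

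**It is a pilot, not designed to determine efficacy.** This bears on precision and on how strongly results are read. It does not remove the need for the analysis to address the stated primary endpoint, and the addition needs no extra men or scans.

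**Conclusion.** The point holds as a mismatch between a focus-level primary endpoint (3.2, and localization in the schema) and a man-level analysis with no location criterion. The interval arithmetic in 7.1 is correct and is not at issue.

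The size cannot be fixed from the documents. Under the assumption of 16/20 correct at man level, the overstatement relative to a location-matched result is 5 points per wrong-site man: 75%, 70% and 65% for one, two and three men, against a reported 80%. If there are no such men, the two figures agree and nothing is lost by showing both. The matched figure should stand beside the man-level one and not replace it, because chance matches rise with the number of foci. The change should be made before PET is compared with histology.

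**What to change.** In Section 7:

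1. Keep man-level accuracy and n=20.
2. Pre-specify a location-matched accuracy beside it, one result per man. A biopsy-positive man is correct only if at least one PET-positive sextant contains a cancer-positive core. A biopsy-positive man with PET uptake but no matching sextant is incorrect. Biopsy-negative men are scored as in the unmatched measure.
3. Define what makes a sextant PET-positive.
4. Report both accuracies with intervals, and the number of PET-positive sextants per man, so the reader can judge how much matching could be chance.

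On the data side, record biopsy histology by the same sextants as the PET form.

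Cost: a few sentences in Section 7 and sextant fields on a biopsy form; the forms readable in 15.2 show sextants for PET only. The matched figure may be lower than the unmatched one. A focus recorded one sextant away through registration error would count as a miss, so adjacent-sextant cases should be listed.

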1.2 Background and Rationale

Cancer is complex yet commonplace, and the most terrifying disease of mankind. Among men in the USA, PC is particularly lethal, second only to cancers of the lung and bronchus combined [1]. In 2010, more than 30,000 men succumbed to PC and more than 240,000 new PC cases were identified in the USA [1]. PC affects one in every 6 men who are 60 years or older and affects African-Americans at a rate 2.4 times greater than European-Americans [1]. Great strides have been made both in diagnosis and treatment of PC. However, the PC-related death rate has not yet declined, and the quality of life of survivors has not yet improved [1]. Three prominent screening tests, the digital rectal examination, MRI, and a blood test for prostate specific antigen (PSA) determination play a significant role in detecting pathologically advanced PC. However, they are not considered reliable tools for early warning of PC [2], [3], [4] nor can they be used reliably to detect recurrent cancer or to determine

metastatic status of the disease. The lack of reliable diagnosis, results in undertreatment or overtreatment of patients with minimal benefit, enormous morbidity, incontinence, and/or impotence. Therefore, histology remains the mainstay of PC confirmation. However, out of >750,000 biopsies performed each year in the USA, >65% show benign pathology, and cost hundreds of millions of health care dollars. Various imaging techniques have been evaluated, but their utility to image suspected PC or its metastatic lesions is not fully dependable [3]. Furthermore, monitoring the effectiveness of PC therapy continues to be a challenge.

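### The 62.5% to 97.5% interval quoted for 80% accuracy in 20 men is a normal-approximation (Wald) interval; small-sample methods put its lower limit about 4 to 6 points lower

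*Combined protocol and SAP*

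**What the plan says.** Section 7.1 (Sample Size Determination; the text runs on under the number 7.2) fixes the sample size: "We will study 20 patients with persistently elevated PSA for a Cu-64 PET imaging in whom biopsy are ordered". It then states the planning assumption, "We expect 80% accuracy in identifying 20 subjects as having histologically determined cancer/absence of cancer", and attaches a precision figure: "The 95% confidence interval of this level of accuracy for this sample size is" plus or minus 17.5%. The next sentence turns the figure into limits: "Thus we expect to find an accuracy level between 62.5% to 97.5"%. It closes with a disclaimer: "Please note this is a pilot study, not designed to be an efficacy determination trial".

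The same figures appear twice in the Study Summary, under Diagnosis and Main Inclusion Criteria and under Statistical Methodology. No interval method is named in any of the three places. The Statistical Methods heading at the end of the sample-size text has nothing under it, and no other section names a method for the final accuracy estimate.

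**The concern.** The interval is symmetric about 80% with only 20 observations and about 4 expected misclassifications (20 × 0.20). In that setting the normal approximation to a binomial proportion is known to cover less than its nominal level, and to sit too high when the proportion is well above one half.

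Three things are at stake.

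- This is the only quantitative support for the sample size. In a study that disclaims efficacy testing, the interval is the main statistical statement.
- Because no method is named for the analysis, the same formula could be carried into the final report by default.
- The sentence that follows uses the confidence limits as a range for the result the study will observe. A confidence interval concerns the unknown true accuracy, given the data. The spread of observed results, given an assumed true accuracy, is a different quantity.

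**Working it through.** **Inputs.** n = 20, expected accuracy p = 0.80 (16 of 20 correct), 95% two-sided, all from section 7.1. All 20 men are assumed evaluable.

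**Reproducing the plan's figure.** The Wald half-width is 1.96 × √(0.80 × 0.20 / 20) = 1.96 × 0.0894 = 0.1753. The limits are 80% ± 17.53 points, or 62.47% to 97.53%, which matches the stated figure. Nearby variants do not match: continuity-corrected Wald gives ±20.0, a multiplier of 2 gives ±17.9, and a t multiplier with 19 degrees of freedom gives ±18.7. The Wald label is therefore inferred from the match.

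**Small-sample intervals for 16/20.** The last two columns show how far the stated limits lie above each alternative, in points.

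| Method | 95% interval | Width | Lower limit | Upper limit |
|---|---|---|---|---|
| Wald (as stated) | 62.5% to 97.5% | 35.1 | – | – |
| Wilson | 58.4% to 91.9% | 33.5 | 4.1 | 5.6 |
| Agresti-Coull | 57.8% to 92.5% | 34.7 | 4.7 | 5.0 |
| Jeffreys | 59.2% to 92.8% | 33.7 | 3.3 | 4.7 |
| Clopper-Pearson | 56.3% to 94.3% | 37.9 | 6.2 | 3.2 |

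Around 80%, Wilson runs −21.6/+11.9 points and Clopper-Pearson −23.7/+14.3. Every alternative is lower at both ends.

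**Exact coverage at n = 20.** This is the sum of Binomial(20, p) probabilities over the counts whose interval contains p.

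| True accuracy | Wald | Wilson | Clopper-Pearson |
|---|---|---|---|
| 0.80 | 92.1% | 95.6% | 97.8% |
| 0.85 | 81.9% | 97.8% | 97.8% |
| Average, 0.70 to 0.90 | 90.4% | 95.5% | 97.7% |

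**Direction of the error.** At a true accuracy of 0.80 the Wald lower limit lies above the truth when 19 or 20 men are classified correctly: 0.0576 + 0.0115 = 6.9%, against a nominal 2.5%. For Wilson and Clopper-Pearson this happens only at 20/20, or 1.2%.

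**If Wald were also used at the end.** Its upper limit would pass 100% at 17, 18 or 19 correct (probability 40.0% at true accuracy 0.80), and its width would be zero at 20/20 (1.2%).

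**The expected-result sentence.** At a true accuracy of 80% the observed count falls between 13 and 19 of 20 (65% to 95%) with probability 95.6%. This is the quantity that sentence describes.

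**Context only.** The plan sets no benchmark. Section 7.1 says "Generally, approximately 60% of the patients with elevated PSA have prostate cancer", so at that rate calling every man positive would be 60% accurate. The stated interval excludes 60%; the Wilson and Clopper-Pearson intervals include it. Section 1.2 gives different biopsy rates (">65% show benign pathology" and "more than 2/3 will find benign pathology"). At those rates, calling every man negative would be about 65% to 67% accurate, which lies inside the stated interval and the small-sample ones alike.

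**The case against.** The strongest reply is that little turns on this. The figure is calculated correctly for its formula. The stated width of 35.1 points exceeds Wilson's 33.5, so precision is not oversold in total; the interval is shifted upward. No hypothesis, threshold or go/no-go rule uses the lower limit, and the plan disclaims efficacy determination. All of that stands, and it limits the weight of the point.

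A second reply is that, read as a planning range for the observed result, the stated limits are sound. The only possible results between 62.5% and 97.5% are 13/20 to 19/20, which carry 95.6% probability at a true accuracy of 80%. This is correct, and it shows that the numbers could be kept under another label. It does not rescue the description of them as a 95% confidence interval.

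A third reply concerns selectivity. Coverage at n = 20 is a sawtooth: Wald recovers to 93.6% at 0.86, and Wilson falls to 93.5% at 0.75 and 92.7% at 0.82. That is fair, and the 81.9% at 0.85 should be read as a low point. The averages, 90.4% against 95.5%, still separate the two methods. The size at the lower limit also depends on the method chosen: adding Wilson with continuity correction (lower limit 55.7%) stretches the range to 3.3 to 6.8 points. All the methods agree on the direction.

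Finally, carrying Wald into the final analysis is a possibility that the plan's silence leaves open, and no section says it will be done.

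**Conclusion.** The concern holds. The plan's only precision figure for 20 men is labelled a 95% confidence interval, but it comes from a method that does not deliver 95% coverage at this sample size. Against the two usual alternatives the lower limit is 4.1 to 6.2 points too favourable and the upper limit 3.2 to 5.6 points too high. The sentence that follows also confuses a confidence interval with a range of expected results.

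This is a fault in the choice of method and in labelling. The sample size stands and no decision in the plan changes, but the figure should be corrected. The conclusion assumes 16 of 20 correct with all 20 men evaluable (fewer would widen every interval) and rests on the inference that the unnamed method is Wald, which the match supports.

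**What to change.** In section 7.1 and in both Study Summary entries, replace the plus-or-minus figure with: if 16 of 20 men are classified correctly (80%), the 95% Wilson confidence interval is 58.4% to 91.9%. Clopper-Pearson, 56.3% to 94.3%, is equally acceptable if guaranteed coverage is preferred.

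Under Statistical Methods, add one sentence naming the same method for the final accuracy estimate.

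If a statement of expected results is kept, label it as such: at a true accuracy of 80%, between 13 and 19 of 20 men (65% to 95%) would be classified correctly with probability 95.6%.

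The cost is three text edits and one added sentence. The quoted lower limit becomes less favourable; enrolment and study procedures do not change.
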